9. STUDY PATIENTS AND DEMOGRAPHICS

9.1 Disposition of Patients and Withdrawals

The numbers and percentage of patients screened, randomized, completing the study, and withdrawing from the study, along with reasons for withdrawal, will be tabulated overall and by treatment group. The number and percentage of patients in each analysis population will be reported. Additionally, the number and percentage of patients that have an investigator-directed dose reduction from two tablets per day to one tablet per day will be summarized. The disposition and withdrawal summaries will be based on all patients who have data entered into the database.

9.2 Protocol Violations and Deviations

Protocol deviations will be checked on complete data for all patients. Protocol deviations will be summarized by type, status as major vs minor, and by treatment group for the Safety population.

Individual patients with protocol deviations or violations will be listed.

9.3 Demographics and Other Baseline Characteristics

Descriptive summaries of the demographic and other baseline characteristics will be completed for all enrolled patients in the study population by treatment groups, unless otherwise specified.

Descriptive summaries of demographic and other baseline conditions will include:

- Demographics (age, gender, race/ethnicity, height, weight, body mass index (BMI), family status, education, employment status, and MINI modules A, C, I, J, K, O)
- Tobacco/nicotine, alcohol, and THC/cannabis use history

Medical History will be coded using a current version of the Medical Dictionary for Regulatory Activities (MedDRA) and summarized by SOC and Preferred Term using frequency counts by treatment group. Physical examination data, as well as findings from dedicated oral cavity examinations, will be presented in listings.

10. EFFICACY ANALYSES

10.1 Primary Efficacy Analysis

10.1.1 Estimand

Population

The analysis population will be patients with PASC as defined by the protocol inclusion/exclusion criteria.

Variable

The primary endpoint will be the change from baseline to Week 14 in the diary NRS weekly average of daily self-reported worst Long COVID pain intensity scores.

Intercurrent Events

For all intercurrent events, data will be analyzed as observed and missing data (both intermittent and following discontinuation) will be assumed to be missing at random. All patients that complete at least one diary pain entry will contribute to the model estimation.

Population-Level Summary

The population-level summary will be the difference in least-square means between treatment arms (analyzed as randomized) at Week 14 from the primary analysis model. See [Section 10.1.2](#) for details.

10.1.2 Primary Analysis

The mean change from baseline in the weekly average of daily pain scores from baseline to each week in the TNX-102 SL and placebo arms will be analyzed using a restricted maximum likelihood (REML) based repeated measures approach without imputation under the assumption that data are missing at random. The model will include the fixed, categorical effects of treatment, study week, and treatment by study week interaction, as well as the fixed covariates of baseline value and baseline value score-by-study week interaction. An unstructured covariance structure will be used to model the within-patient errors. If this analysis fails to converge, the following structures will be tested in this order: first order ante dependence, heterogeneous first order autoregressive, heterogeneous compound symmetry and compound symmetry with the first to give convergence used. The Kenward-Roger approximation will be used to estimate the denominator degrees of freedom (DDFM) with the unstructured matrix; other covariance structures will utilize the sandwich matrix and the SAS® default DDFM. Week 14 will serve as the primary time point of interest. Significance testing will be based on least-squares means and two-sided 95% confidence intervals will be presented. The p-values will be compared against a two-sided alpha of 0.05.

10.1.3 Sensitivity Analysis

The following sensitivity analysis may be performed:

Data will be imputed using multiple imputation as described in [Section 8.1.4](#). Models identical to the primary analysis described above will be fit for the 20 MI repeated sets; LS means and

differences across the twenty MI reps will be combined using SAS® procedure MIANALYZE ([Rubin, 1976](#)). Week 14 will serve as the primary time point of interest. Significance testing will be based on least-squares means and two-sided 95% confidence intervals will be presented. The p-values will be compared against a two-sided alpha of 0.05.

10.2 Secondary and Exploratory Efficacy Analyses

Secondary efficacy analyses will be based on the ITT population only.

10.2.1 Continuous Key Secondary Endpoints

For the purposes of possible label claims and reported p-values entered into the multiplicity algorithm, an approach identical to the primary analysis will be used for all continuous outcomes. See Section 10.1.2 for the analysis approach.

Outcomes using these analyses will include:

- Change from Baseline in the weekly average of the daily diary NRS assessment of sleep quality at the Week 14 endpoint
- Change from Baseline in the PROMIS score for fatigue at the Week 14 endpoint
- Change from Baseline in the PROMIS score for cognitive function at the Week 14 endpoint

For each, all time points will be summarized, but the primary time point of interest is Week 14. Time points other than Week 14 are considered exploratory. The estimand for each is identical to the primary, substituting for the endpoint in question.

This will be repeated on the outcomes above, but using observed data only without imputation.

For the sleep quality assessment collected via a daily patient diary, the baseline score and the weekly scores for each patient will be calculated as the weekly average score based on the mean of the scores recorded for that study week ([Section 8.2.2](#)).

10.2.2 Other Continuous Secondary and Exploratory Endpoints

Descriptive statistics will be reported for each endpoint, time point and treatment for both the observed values and the changes from baseline.

The with the exception of ISI and PCFS (collected just once post-baseline), change from baseline in each endpoint from baseline to each visit in the TNX-102 SL and placebo arms will be analyzed using a restricted maximum likelihood (REML) based repeated measures approach with no imputation. Week 14 will serve as the primary time point of interest. Models will include the fixed, categorical effects of treatment, study week, and treatment by study week interaction, as well as the fixed covariates of baseline value and baseline value score-by-study week interaction. An unstructured covariance structure will be used to model the within-patient errors. If this analysis fails to converge, the following structures will be tested in this order: first order ante dependence, heterogeneous first order autoregressive, heterogeneous compound symmetry and compound symmetry with the first to give convergence used. The Kenward-Roger approximation will be used to estimate the denominator degrees of freedom (DDFM) with the unstructured matrix; other covariance structures will utilize the sandwich matrix and the SAS®

default DDFM. Significance testing will be based on least-squares means and two-sided 95% confidence intervals will be presented.

For ISI and PCFS, an ANCOVA model will be fit on the change from baseline to Week 14. Fixed effects will include categorical effects for treatment and a covariate for the baseline value of each scale. Significance testing will be based on least-squares means and two-sided 95% confidence intervals will be presented.

Secondary Efficacy Endpoints analyzed this way will include:

- Change from Baseline to Week 14 in the Sheehan Disability Scale (SDS)
- Change from Baseline in the Patient Reported Outcomes Measurement Information System (PROMIS) score for sleep disturbance at the Week 14 endpoint
- Change from Baseline to Week 14 in the Insomnia Severity Index (ISI)
- Change from Baseline to Week 14 in the Epworth Sleepiness Scale (ESS)

Exploratory endpoints analyzed this way will include:

- Patient Global Impression of Change (PGI-C) Scored 1-7 at Week 14 (without the fixed covariates of baseline value and baseline value score-by-study week interaction)
- Change from Baseline in the PROMIS score for sleep disturbance at each post-randomization clinic visit
- Change from Baseline in the PROMIS score for fatigue at each post-randomization clinic visit
- Change from Baseline in the PROMIS fatigue symptom questions 1,3,4 (individually and summed) at each post-randomization clinic visit
- Change from Baseline in the PROMIS fatigue impact questions 6,7,8 (individually and summed) at each post-randomization clinic visit
- Change from Baseline in the PROMIS score for cognitive function at each post-randomization clinic visit
- Change from Baseline in the weekly average of the daily diary assessment of sleep quality at Weeks 1-14
- Change from Baseline in the weekly average of the daily diary assessment of worst pain intensity scores at Weeks 1-14
- Change from Baseline in laboratory markers of inflammation
- Change from Baseline to Week 14 in the Post-COVID-19 Functional Status Scale (PCFS)
- Change from Baseline in the total number of the modified Michigan Body Map pain regions identified as having pain at each post-randomization clinic visit
- Change from Baseline in average NRS Long COVID pain intensity across the 7 pain regions in modified Michigan Body Map at each post-randomization visit

- Change from Baseline in average NRS Long COVID pain intensity within the index site region on the modified Michigan Body Map at each post-randomization visit
- Change from Baseline in average NRS Long COVID pain intensity within the worst region for a given visit on the modified Michigan Body Map at each post-randomization visit

As noted above, results of Week 14 are of primary interest, with other time points being exploratory. For PROMIS fatigue, the questions regard symptoms and impacts will be analyzed independently and additional post-hoc analyses may be completed to evaluate how they contribute to the overall score.

10.2.3 Categorical Endpoints

A categorical analysis of PGI-C will compare the treatment arms with a difference in proportions Z test (equivalent to a Pearson's Chi Squared). Patients with results of "very much improved" or "much improved" (defined as responders) will be compared to all other categories (defined as non-responders). Patients with missing data will be considered non-responders. The percentages of responders and the 95% CIs of the percentages as well as the difference in the percentages and its 95% CI will be reported. In the case of sparse data (<5 patients expected in a cell), Fisher's exact test will be employed. A summary of frequency counts for all PGI-C responses for each time point will be presented; Week 14 is of primary interest and all other time points are considered exploratory.

Exploratory analyses of the following endpoints will use identical methodology as the PGI-C analysis:

- Proportion of patients with a $\geq 30\%$ improvement from Baseline to Weeks 1–14 in the daily self-reported worst Long COVID pain intensity score
- Proportion of patients with a $\geq 50\%$ improvement from Baseline to Weeks 1–14 in the daily self-reported worst Long COVID pain intensity scores

The number and percentage of patients in each PCFS category will be reported at each visit where it is collected.

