13.6. Secondary Efficacy Analyses

Secondary efficacy analyses will be based on the ITT population. For the purposes of possible label claims and reported p-values entered into the multiplicity algorithm, an approach identical to the primary analysis will be used for all key secondary continuous outcomes.

Analyses of other continuous secondary endpoints will be similar to the analysis of the primary endpoint, utilizing MMRM, but without MI for missing data. Significance tests of treatment

differences will be based on least-squares means, and corresponding 95% confidence intervals will be calculated.

A categorical analysis of PGIC will compare the treatment arms with a difference in proportions Z test (equivalent to a Pearson's Chi Squared). Subjects with results of "very much improved" or "much improved" (defined as responders) will be compared to all other categories (defined as non-responders). Subjects with missing data will be considered non-responders. The percentages of responders and the 95% CIs of the percentages as well as the difference in the percentages and its 95% CI will be reported. A summary of frequency counts for all PGIC responses for each time point will be presented; Week 14 is of primary interest and all other time points are considered exploratory.

To adjust for multiplicity and to control for overall type I error, a sequential test procedure will be applied to the primary and key secondary efficacy endpoints. If the primary analysis produces a result that is statistically significant at the two-sided 0.046 level, a significance level of 0.046 will be used for comparing the key secondary endpoints in an ordered fashion. If the analysis for a key secondary endpoint does not produce a statistically significant result at the 0.046 level, then the remaining key secondary endpoint analyses will automatically be considered non-significant regardless of the p-value produced. In the case of an early stop for efficacy, this will be the same as the stopping criteria for the primary efficacy endpoint (secondary endpoints will be tested at p-value = 0.005, one-sided).

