3.2.2 Secondary Endpoints

Key secondary efficacy endpoints include:

- Change from Baseline in the weekly average of the daily diary NRS assessment of sleep quality at the Week 14 endpoint
- Change from Baseline in the PROMIS score for fatigue at the Week 14 endpoint
- Change from Baseline in the PROMIS score for cognitive function at the Week 14 endpoint

Other secondary efficacy endpoints include:

- Change from Baseline in the Patient Reported Outcomes Measurement Information System (PROMIS) score for sleep disturbance at the Week 14 endpoint
- Proportion of patients with a Patient Global Impression of Change (PGI-C) rating of “very much improved” or “much improved” at the Week 14 endpoint
- Change from Baseline to Week 14 in the Sheehan Disability Scale (SDS)
- Change from Baseline to Week 14 in the Insomnia Severity Index (ISI)
- Change from Baseline to Week 14 in the Epworth Sleepiness Scale (ESS)

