4.2 Method of Treatment Assignment and Randomization

The following randomization criteria must be satisfied at the Baseline visit (Visit 2) to be eligible for randomization:

1. Continues to meet all inclusion and exclusion criteria, including urine and blood test results, and is successfully and consistently utilizing the diary system.
2. Patient's pain satisfies the following criteria, as assessed by diary pain scores (24-hour recall):

- a. A mean worst daily Long COVID pain intensity score ≥ 4 and ≤ 9 on the 11-point (0–10) NRS for the 7 days immediately preceding Visit 2, and
- b. No more than 2 individual days with a Long COVID pain score < 4 on the 7 days immediately preceding Visit 2, and
- c. No score of 10 on any of the 7 days immediately preceding Visit 2, and
- d. Long COVID pain scores recorded on at least 5 out of the 7 days immediately preceding Visit 2

Patients will be randomly assigned to receive TNX-102 SL or matching placebo sublingual tablet in a 1:1 ratio.

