8.1.1.2 Multiplicity

To adjust for multiplicity and to control for overall type I error, a sequential test procedure will be applied to the primary and key secondary efficacy endpoints. If the primary analysis produces a result that is statistically significant at the two-sided 0.05 level, a significance level of 0.05 will be used for comparing the key secondary endpoints in an ordered fashion. If the analysis for a key secondary endpoint does not produce a statistically significant result, then the remaining key secondary endpoint analyses will automatically be considered non-significant regardless of the p-value produced.

The order of key secondary endpoints in which they are to be tested is as follows:

- Change from Baseline in the weekly average of the daily diary NRS assessment of sleep quality at the Week 14 endpoint
- Change from Baseline in the PROMIS score for fatigue at the Week 14 endpoint
- Change from Baseline in the PROMIS score for cognitive function at the Week 14 endpoint

No other adjustments for multiplicity will be made and other p-values displayed in the output will be considered for descriptive summary purposes only and will not be used for formal inference. Additional details regarding statistical analysis for the listed endpoints can be found in [Section 10](#).

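### The PGI-C and pain-responder comparisons use no baseline covariate: a modest, avoidable loss of precision

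*SAP*

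**What the plan says.** - **PGI-C responders (an other secondary endpoint in SAP 3.2.2).** SAP 10.2.3: "A categorical analysis of PGI-C will compare the treatment arms with a difference in proportions Z test", with Fisher's exact test when expected cell counts are small and missing ratings counted as non-response. Protocol 13.6 specifies the same comparison: "A categorical analysis of PGIC will compare the treatment arms with a difference in proportions Z test".
- **30% and 50% pain responders (exploratory).** SAP 10.2.3: "Exploratory analyses of the following endpoints will use identical methodology as the PGI-C analysis".
- **PGI-C scored 1–7 (exploratory).** SAP 10.2.2 fits the repeated-measures model "without the fixed covariates of baseline value and baseline value score-by-study week interaction". That leaves treatment, week and their interaction.
- **Change-from-baseline endpoints.** These are all adjusted for their own baseline. The primary model in SAP 10.1.2 has treatment and week effects "as well as the fixed covariates of baseline value and baseline value score-by-study week interaction". The key secondary and other repeated-measures endpoints follow the same form, and ISI and PCFS use ANCOVA with the baseline value.
- **Availability of baseline pain.** SAP 4.2 makes it a condition of randomisation: "Long COVID pain scores recorded on at least 5 out of the 7 days immediately preceding Visit 2".
- **Status of the p-values.** SAP 8.1.1.2, on everything outside the primary and key secondary sequence: "other p-values displayed in the output will be considered for descriptive summary purposes only".

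**The concern.** The plan adjusts for baseline wherever an endpoint has its own baseline value, and uses no covariate at all for the responder endpoints and PGI-C 1–7. PGI-C has no pre-treatment value, since Protocol Table 2 first schedules it at Week 2. That explains why its own baseline term is dropped, but not why no other baseline measure replaces it. The PGI-C item (Protocol Appendix 10) asks about Long COVID symptoms including pain, so baseline pain is a natural predictor, and it is already collected.

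What is at stake is the width of the intervals on these endpoints. This matters somewhat more because SAP 8.1.1.1 lets the trial claim proof of concept on an observed primary effect size above 0.20 without statistical significance. No hierarchy or threshold then applies to the secondary endpoints, and they would be read as estimates with intervals.

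**Working it through.** **Inputs.** From SAP 6: 235 per arm, standardised effect 0.3, two-sided alpha 0.05. Assumed, because the documents give neither: the correlation r between baseline pain and outcome (0.2 to 0.3 as the working range, 0.5 as a high case), and a 30% control response rate.

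**1. The plan's own figure.** Power = Φ(0.3 × √(235/2) − 1.960) = Φ(3.252 − 1.960) = Φ(1.292) = 90.2%. The noncentral t with 468 df gives 90.1%. The stated 90% reproduces. It concerns the primary endpoint only; no power is stated for PGI-C or the pain responders.

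**2. PGI-C 1–7, treated as a single time point.** Adjustment multiplies the outcome SD by √(1 − r²). Power = Φ(3.252/√(1 − r²) − 1.960), and the gain in equivalent sample size is 1/(1 − r²) − 1.

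| r | √(1 − r²) | Power | Equivalent extra patients |
|---|---|---|---|
| 0 | 1.000 | 90.2% | 0% |
| 0.2 | 0.980 | 91.3% | 4% |
| 0.3 | 0.954 | 92.6% | 10% |
| 0.5 | 0.866 | 96.4% | 33% |

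**3. Responder endpoints.** A latent shift of 0.3 SD from a 30% control rate gives Φ(−0.524 + 0.3) = 41.1%. The formula power of the unadjusted Z test is then 71%. Simulation used 6,000 trials per row at 235 per arm, with r on the latent scale. It compared the Z test with a baseline-adjusted risk difference from a linear model with baseline and treatment-by-baseline terms and robust standard errors. That model stands in for the standardised logistic estimate.

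| r | Z test | Adjusted | Gain (points) | Variance ratio, adjusted/unadjusted |
|---|---|---|---|---|
| 0 | 71.4% | 71.7% | 0.3 | 1.00 |
| 0.2 | 70.9% | 72.2% | 1.3 | 0.97 |
| 0.3 | 70.2% | 73.4% | 3.2 | 0.95 |
| 0.5 | 72.1% | 79.0% | 6.9 | 0.86 |

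The Monte Carlo standard error of each power is about √(0.71 × 0.29/6000) = 0.6 points, which accounts for the drift in the Z-test column. The 0.3 points at r = 0 owe nothing to the covariate.

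**4. Validity.** Under no treatment effect the Z test rejected in 4.8% to 5.7% of trials across the four values of r, averaging 5.1%. Under the alternative, the mean unadjusted and adjusted risk differences agreed at about 0.111.

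**5. Chance imbalance.** The standard error of the between-arm difference in mean baseline pain is √(2/235) = 0.092 SD. The probability of a difference above 0.2 SD is 2 × (1 − Φ(0.2/0.092)) = 3%; above 0.3 SD it is 0.1%. Imbalance reaches the outcome only after multiplication by r. At r = 0.3, a 0.2 SD imbalance moves PGI-C 1–7 by 0.06 SD, against a standard error of 0.092 SD for the outcome contrast. This is the same loss as in step 2 seen from another side, not an addition to it.

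**The case against.** A pre-specified two-proportion comparison with a risk difference and interval is a standard analysis, randomisation makes it valid, and protocol and SAP agree on it. No formal decision rests on these endpoints. The pain-responder definitions already use baseline as the denominator, and the continuous pain data behind them are baseline-adjusted in the primary model. The size of any gain depends on a correlation that the documents do not supply. All of this stands, and it sets the weight of the point. It does not remove it: the arm comparison of responders is still unadjusted, and the covariate is already collected.

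Three stronger readings are tempting, and the documents support none of them.

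- **That the unadjusted comparisons are biased, or that imbalance passes in full into the result.** Step 4 shows neither bias nor inflated error, and step 5 shows that imbalance enters only in proportion to r.
- **That the trial is small enough for imbalance to be a serious threat.** SAP 13 mentions low patient counts across sites as the reason for dropping the site covariate, but the text available gives no reduced total; the only stated size is 470. Even at an assumed 50 per arm, where a difference above 0.3 SD has a 13% chance, such an imbalance at r = 0.3 moves PGI-C 1–7 by 0.09 SD against a standard error of √(2/50) = 0.20 SD.
- **That dropping site took a safeguard away from the PGI-C responder test.** The Z test in Protocol 13.6 never included site.

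There is also a fair objection to a larger remedy. A main logistic model that adds baseline PROMIS scores could run into sparse data. It could also lose patients whose PROMIS baseline is missing, since SAP 4.2 does not require those scores for randomisation. That argues for baseline pain alone, in a supportive role.

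**Conclusion.** The point holds as a matter of efficiency. One other secondary endpoint and a small group of exploratory ones are compared without any baseline covariate, although baseline diary pain is available for every patient randomised per protocol. The analyses as written are valid and their p-values descriptive.

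At 235 per arm and r of 0.2 to 0.3, the forgone gain is about 1 to 3 power points for responders, and the equivalent of about 4% to 10% more patients for PGI-C 1–7. The correlation, the 30% control rate, the 0.3 SD latent shift for responders and the single-time-point simplification for PGI-C 1–7 are assumptions. A correlation of 0.5 would raise the gains to about 7 points and 33%; a correlation near zero would leave almost none.

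**What to change.** - **SAP 10.2.2, PGI-C 1–7:** add baseline diary pain and its interaction with study week as fixed covariates.
- **SAP 10.2.3, PGI-C and 30%/50% pain responders:** keep the Z or Fisher test as written. Beside it, pre-specify a logistic model with treatment and baseline diary pain only. Report the standardised risk difference with a 95% CI, naming the interval method (delta method or bootstrap). Leave missing counted as non-response. State that the Z or Fisher result stands alone if data are sparse or the model does not converge.

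The PGI-C comparison in Protocol 13.6 is untouched, and Protocol 13.6.1 already leaves exploratory analyses to the SAP. The change should be made before unblinding. It costs some SAP wording, a little programming and a second estimate to report for each responder endpoint. No new data are needed.
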